### **1.4 Current Therapies and Unmet Medical Need**

There is no standard treatment for hemophilic pseudotumor; factor replacement therapy and surgical excision are the primary treatment options [van Ommeren, Mooren et al. 2000]. In

countries lacking significant medical resources, FVIII prophylaxis and surgical intervention are rarely feasible due to availability of factor replacement, lack of local expertise and/or inability to perform the intervention due to extent or site of the pseudotumor. Due to the limited medical resources, hemophilic pseudotumor has a higher incidence in these countries.

It is hypothesized that an agent that confers a consistent FVIII-equivalent level in the mild deficient range that is not associated with trough levels below 10% will confer a higher degree of hemostasis in patients with pseudotumors. It is not practical to achieve such high trough levels over long periods of time using standard factor replacement therapy; instead new products, such as Hemlibra (emicizumab) may provide an alternative approach. If a higher degree of hemostasis is achieved, this is expected to result in a decreased rate of breakthrough bleeding requiring intermittent hemostatic therapy, and an associated decrease in uncontrolled bleeding resulting in anemia, transfusion, and hospitalization. If these endpoints are achieved it is also hypothesized that activity and quality of life may increase or improve respectively.

## 2 STUDY OBJECTIVES

### 2.1 Primary Objectives

The primary objective of the study is:

- To determine the hemostatic efficacy\* of prophylactic weekly injections of Hemlibra (emicizumab) in hemophilia A subjects (baseline FVIII level <40%) with pseudotumor, with or without FVIII inhibitors.

### 2.2 Secondary Objectives

The secondary objectives of the study are:

- To determine the rate of breakthrough bleeding events, either related or unrelated to the pseudotumor, requiring alternate hemostatic therapy
- To evaluate the control of progression, stabilization or regression (ie, change in size) of the pseudotumor
- To determine the safety of Hemlibra (emicizumab) based on adverse events (AEs) and serious adverse events (SAEs) including lack of efficacy and development of anti-drug antibodies (ADA). Samples for ADA will be banked for analysis and performed in conjunction with Genentech/Roche either yearly, at the end of the study, or as determined by the Study Investigator based upon any reported lack of clinical efficacy
- To evaluate the change in quality of life and activity as measured by the Haem-A-QoL and EQ-5D-5L with Hemlibra (emicizumab) prophylaxis. If an activity monitoring device is standardly utilized by the patient (eg, Fitbit) then data from that device will be requested from the patient to assist in activity monitoring as well
- To evaluate the effect of Hemlibra prophylaxis on any surgical procedures, including the use of other hemostatic agents such as FVIII, aPCC or rFVIIa and overall hemostatic efficacy

---

\* Hemostatic efficacy is defined as the rate of breakthrough bleeding related to the pseudotumor; which is defined as the number of bleeding episodes while on Hemlibra that require alternative hematologic therapy.

## 3 INVESTIGATIONAL PLAN

### 3.1 Overall Study Design and Plan

This is a single arm, phase 4, prospective, open-label, US single-center study to assess the hemostatic efficacy and safety of Hemlibra (emicizumab) for hemostatic control of hemophilia A patients (baseline FVIII level <40%), children and adults, with and without inhibitors with hemophilic pseudotumors. The study is not randomized.

Subjects will be consented and screened at the IHTC and will be eligible for study participation if they meet all inclusion criteria. Subjects will be excluded from the study if they meet any of the exclusion criteria. US-labeled Hemlibra (emicizumab) will be administered using the FDA-approved once-weekly dosing regimen for loading dose and prophylactic dose. Subjects will administer Hemlibra (emicizumab) for a minimum of 2 years, except in the case of subject withdrawal or early termination of the study, and a maximum of 4 years. Breakthrough bleeding episodes will be treated using the local standard of care subject to the conditions listed in **Sections 5.1.2 and 5.4**.

The proposed study is seeking to address the following knowledge gaps:

- Does weekly prophylactic Hemlibra (emicizumab) reduce the rate of bleeding events in subjects with hemophilia A and pseudotumor, including the rate of hospitalization, anemia and transfusion?
- Does weekly prophylactic Hemlibra (emicizumab) control the progression, stabilization or regression (ie, affect the size) of the hemophilic pseudotumor?
- Does weekly prophylactic Hemlibra (emicizumab) result in an increase in QoL and activity level?

#### 3.1.1 Initial Study Visit (Consent and Screening)

The initial study visit will take place at the IHTC and will comprise subject consent and screening. The subject will be screened per the criteria listed in **Section 4** of this protocol and will include a physical examination and the review/collection of clinical and laboratory data (if not included in the subject's medical records) including:

- Baseline FVIII,\* aPTT, PT and VWF:Ag
- Baseline FVIII inhibitor level
- Baseline CBC w/diff and CMP + direct bilirubin
- Vital signs (blood pressure, pulse, temperature, and respiratory rate) and weight

---

\* If the subject has an inhibitor, then testing for FVIII level may not be medically necessary as FVIII is usually undetectable in such cases. Exceptions exist, such as for a patient who has mild hemophilia with an inhibitor that only recognizes infused FVIII and not endogenous FVIII.

- Serum pregnancy test for female subjects
- Documentation of current or past infection of Hepatitis A, B and C (tests listed below). If documentation is not available, then the tests will be administered as part of the screening process\*
  - HAV:Ab
  - HBV:Ag and Ab (Core and Surface); if HBV:Ag positive, HBV viral load
  - HCV:Ab; if HCV:Ab positive, HCV viral load
- Documentation of HIV infection (if Ab positive, viral load and CD4 count)
- Baseline Haem-A-QoL and EQ-5D-5L
- If an activity monitoring device is standardly utilized by the patient, then permission will be requested to access data for the 1-month period prior to study entry and use of data from the device if continued during the study
- Review of at least 16 weeks, and up to 6 months if available, of data on prior use of hemostatic therapy and number of breakthrough bleeding events
- Review of 6 months of data on prior need for hospitalization or for PRBC transfusion
- Review of therapy prior to study entry with dose and interval and trough level if available on prophylaxis
- Review of history of inhibitor including date of first positive test, highest documented titer and date
- Review of concomitant medications and supplements
- Determination of the date of development or identification of pseudotumor and documentation of radiologic (CT or MRI) scans
- Review of surgeries and procedures

If the subject is not vaccinated, previously exposed, or immune to HAV and/or HBV then they will receive the first dose of the HAV and/or HBV vaccine during screening. Subjects must follow up with their local provider to complete the recommended vaccination schedule.†

Safety data reporting will commence at the time of subject consent and study procedures and will end at study discontinuation/termination or 24 weeks following the last administration of study treatment, whichever occurs first. Extensions to this time will be made in certain situations (eg, **Sections 6.11.3.2.f and 6.11.3.2g**).

---

\* Although this testing and documentation is considered standard of care, there are important reasons to include this in the study and budget. There are patients in the US who are not followed at a federally recognized hemophilia treatment center and this testing may be inconsistently available. In addition, there are patients who refuse entry into CDC studies where this testing is performed or refused vaccination to prevent Hepatitis A and/or B transmission. Knowing each patient's viral exposure status and vaccination history will be important to decrease risk of community acquired infections that may lead to development of AEs that could be avoided.

† Vaccinations will not be charged to the study.

Screening is expected to take up to 10 days but may be shorter depending on the return of required laboratory testing. If successfully screened, the subject may then be enrolled in the study and receive Hemlibra (emicizumab) loading doses during the second study visit

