### 4.2 Inclusion Criteria

Patients must meet the following criteria for study entry:

- Signed informed consent form from the subject, parent or guardian
- Diagnosis of congenital hemophilia A (baseline FVIII level <40%) with or without FVIII inhibitor, either high or low responding, regardless of titer
- Diagnosis of a hemophilic pseudotumor confirmed by radiologic assessment such as CT or MRI
- Any weight or BMI
- Medical documentation of prophylactic or episodic treatment (FVIII or bypassing agent) and the number of bleeding episodes for at least 16 weeks, and up to 6 months if available, prior to entry into the study
- Medical documentation of any need for PRBC transfusion or hospitalization for 6 months prior to entry into the study
- Subjects with a history of an inhibitor should provide documentation of the inhibitor history including date of initial diagnosis of inhibitor, peak titer, and agent utilized for hemostatic control
- Subjects with high titer inhibitors or those with low titer inhibitors who do not respond to FVIII must be willing to use rFVIIa as first line therapy for the treatment of breakthrough bleeding events
- Medical documentation of ITI therapy for subjects with a history of a FVIII inhibitor and ITI, including current FVIII inhibitor titer
- Willingness to discontinue any current prophylactic hemostatic regimen (FVIII or bypassing agent) and/or FVIII ITI therapy for the duration of the study
  - Subjects receiving FVIII prophylaxis must be willing to discontinue their FVIII prophylactic regimen immediately prior to their second loading dose of Hemlibra (emicizumab)
  - Subjects receiving bypassing agent prophylaxis must be willing to discontinue their prophylactic regimen at least 24 hours prior to their first loading dose of Hemlibra (emicizumab)

- Subjects receiving FVIII ITI therapy must be willing to discontinue ITI immediately prior to their first loading dose of Hemlibra (emicizumab)
- Willingness and ability to comply with scheduled visits, treatment plans, laboratory tests, and other study procedures, including the health-related questionnaires, activity tracking, and bleed diaries, using systems provided during the study

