#### 4.3 Exclusion Criteria

Subjects who meet any of the following criteria will be excluded from study entry:

- Inherited or acquired bleeding disorder other than congenital hemophilia A
- Lack of a documented diagnosis of hemophilic pseudotumor
- Patients who are at high risk for TMA (eg, have a previous medical or family history of TMA), in the Study Investigator's judgment
- History of illicit drug or alcohol abuse within 48 weeks prior to screening, in the Study Investigator's judgment
- Previous (within the last 12 months) or current treatment for thromboembolic disease (with the exception of previous catheter-associated thrombosis for which anti-thrombotic treatment is not currently ongoing) or signs of thromboembolic disease
- Other conditions (eg, certain autoimmune diseases) that may currently increase the risk of bleeding or thrombosis

---

\* Vaccinations will not be charged to the study.

- History of clinically significant hypersensitivity associated with monoclonal antibody therapies or components of the Emicizumab injection
- Planned surgery (excluding minor procedures such as tooth extraction or incision and drainage) during the study
- Known HIV infection with CD4 counts <200 cells/ $\mu$ L. HIV infection with CD4 counts  $\geq$ 200 cells/ $\mu$ L permitted
- Use of systemic immunomodulators (eg, interferon) at enrollment or planned use during the study, with the exception of anti-retroviral therapy
- Concomitant disease, condition, significant abnormality on screening evaluations or laboratory tests, or treatment that could interfere with the conduct of the study, or that would, in the opinion of the Study Investigator, pose an additional unacceptable risk in administering study drug to the patient
- Receipt of any of the following:
  - Hemlibra (emicizumab) in a prior investigational study
  - An investigational drug to treat or reduce the risk of hemophilic bleeds within 5 half-lives of last drug administration
  - A non-hemophilia-related investigational drug within last 30 days or 5 half-lives, whichever is shorter
  - Any other investigational drug currently being administered or planned to be administered
- Inability to comply with the study protocol in the opinion of the Study Investigator
- Pregnancy or lactation or intention to become pregnant during the study
- Women with a positive serum pregnancy test result within 10 days prior to initiation of study drug

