## 5.5 Restrictions

Use of the following therapies may be prohibited for subjects enrolled in ongoing studies and for at least 4 weeks prior to the initiation of study treatment.

- Use of drugs that would affect hemostasis (eg, aspirin, non-steroidal anti-inflammatory drugs, or anticoagulants [other than to flush, dwell, or de-clot a central venous access device]) but excluding drugs intended to control bleeding episodes or used in the context of minor surgery (eg, tooth extraction) or injuries (eg, concussion) to prevent deterioration
- Use of systemic immunomodulators (eg, rituximab, interferon) other than antiretroviral therapy from enrollment to last observation
- Elective surgery (excluding minor procedures such as tooth extraction, central venous access device removal, or incision and drainage as well as emergency surgeries) from enrollment to last observation

- Use of aPCC for short-term or long-term prophylaxis
- Use of antifibrinolytics concomitantly with aPCC
- Use of other investigational drugs from enrollment to last observation

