### 6.2 Medical History/Demographics

The medical history of the subject will be obtained. Specific information will be recorded on the CRF relating to any prior or existing medical conditions/surgical procedures involving the following: Infectious Diseases (including viral infections, such as Hepatitis and HIV), Allergies, Metabolic/Endocrine/Nutritional, Hematopoietic, Musculoskeletal, Dermatologic, Head, Ears, Eyes, Nose, and Throat (HEENT), Breasts, Respiratory, Cardiovascular, Gastrointestinal/Hepatic, Genitourinary/Renal, Neurologic, and Psychiatric/Psychosocial.

Specific documentation for the following should be provided to the IHTC:

- Medical documentation of any prophylactic (FVIII or bypassing agent) therapy for at least 16 weeks, and up to 6 months if available, prior to entry into the study
- Medical documentation for the number of bleeding episodes (including location, severity, duration and treatment) for at least 16 weeks, and up to 6 months if available, prior to entry into the study. If available, the hemostatic agent, number of infusions and quantity of drug infused for each bleeding episode will be collected
- Medical documentation of any complications related to the pseudotumor (including any incidences of anemia, the need for PRBC transfusion or hospitalization) for 6 months prior to entry into the study

- Subjects with a history of an inhibitor should provide documentation of the inhibitor history including date of initial diagnosis of inhibitor, peak titer, and agent utilized for hemostatic control
- Medical documentation of ITI therapy for subjects with a history of a FVIII inhibitor and ITI, including current FVIII inhibitor titer
- Documentation of current concomitant medications and supplements
- Date of development or identification of pseudotumor and documentation of radiologic (CT and/or MRI) scans

Demographics (date of birth, race/ethnicity, gender, height, weight, etc) and vital signs (blood pressure, pulse, temperature, and respiratory rate) will also be collected.

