### 9.5 Primary Endpoints

The primary endpoints are:

- The number of breakthrough bleeding events over time requiring the use of alternate hemostatic therapy (bleed rate) related to the pseudotumor
- The number of hospital admissions related to the pseudotumor
- The number of incidences of anemia requiring transfusion or intervention related to the pseudotumor
- The control of progression, stabilization or regression of the pseudotumor (ie, changes in size) as measured by yearly assessments including CT and/or MRI

The study investigator will determine whether the reported event was related to the pseudotumor based on a retrospective review of the medical data (eg, bleed location, patient symptoms, etc).

Efficacy analyses will be performed based on the parameters listed above. As there is no control group or placebo in the study, the on-study data will be compared to that listed in the subject's

medical files prior to study enrollment. The efficacy analyses will exclude data acquired during the 4 loading doses (study visit 2). Analyses will be performed on a per-subject basis and in aggregate. Sub-analyses will be considered based upon the included study population.

Demographic and baseline characteristics for all subjects will be summarized using descriptive statistics for continuous variables and frequencies and percentages for categorical variables.

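### Stays for planned pseudotumor surgery are not separated in the 6-month baseline but are screened out and restricted on study, so admissions and transfusion-requiring anemia can appear to fall with no drug effect

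*Combined protocol and SAP*

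**What the plan says.** **Pre-study side.** Section 3.1.1 calls for a "Review of 6 months of data on prior need for hospitalization or for PRBC transfusion", and the inclusion criterion in 4.2 requires "Medical documentation of any need for PRBC transfusion or hospitalization for 6 months prior to entry into the study". Neither distinguishes a stay for a planned operation from one forced by bleeding. Section 6.2 is narrower and asks, over the same 6 months, for "Medical documentation of any complications related to the pseudotumor (including any incidences of anemia, the need for PRBC transfusion or hospitalization". Screening also includes a "Review of surgeries and procedures", but nothing ties that review to the endpoint counts. Section 1.4 states that "factor replacement therapy and surgical excision are the primary treatment options", and no entry criterion excludes a subject who was recently operated on.

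**On-study side.** Section 4.3 excludes candidates with "Planned surgery (excluding minor procedures such as tooth extraction or incision and drainage) during the study". Section 5.5 lists among its restrictions "Elective surgery (excluding minor procedures such as tooth extraction, central venous access device removal, or incision and drainage as well as emergency surgeries", running from enrollment to the final observation. The lead-in to 5.5 says only that the listed items may be disallowed. It also mentions a period of at least 4 weeks before treatment starts. Section 3.1.5 has every on-study surgery recorded as planned or unplanned.

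**Comparison.** Section 9.5 lists four primary endpoints. Two of them are pseudotumor-related admissions and pseudotumor-related anemia that needs transfusion or intervention. With no control group, the "on-study data will be compared to that listed in the subject's" medical files from before enrollment, and only loading-dose data are left out. Section 6.10 makes the same before/after comparison the basis for judging efficacy. The investigator decides relatedness by retrospective review, and no rule covers surgical stays.

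**The concern.** A before/after comparison without a control is informative only if the same kinds of event can be counted on both sides. Here, one kind of event is open to capture before entry and largely kept out afterwards: an admission for planned pseudotumor surgery, with any transfusion that went with it. The reason is who may enter and what is restricted on study, not the drug. Any resulting bias favors emicizumab.

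The baseline is short and the sample is about 10 subjects, so one or two such stays could account for much of an apparent fall. The analysis is descriptive, and neither 6.10 nor 9.5 contains a step that would separate the two explanations.

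**Working it through.** The plan gives no figure to reproduce. Section 9.2 sets the sample size at about 10 by feasibility, and no event rate, effect size or test is stated. The check is therefore person-time arithmetic under an assumed absence of drug effect.

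**Inputs from the documents**
- Subjects: about 10 (9.2).
- Baseline window for admissions and transfusion: 6 months (3.1.1, 4.2).
- Baseline person-time: 10 × 0.5 = 5 person-years.

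**Assumptions, since the documents give no values**
- b: rate of pseudotumor-related admissions that are not for planned surgery, per person-year, identical before and on study.
- s: number of planned pseudotumor-surgery stays in the baseline window that the investigator judges related.
- No planned-surgery stays on study. Any that did occur would shrink the effect.

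**Formula.** The baseline rate is b + s/5 and the on-study rate is b. The apparent reduction is (s/5) / (b + s/5). Each stay adds 1/5 = 0.2 per person-year to the baseline.

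| b per year | s = 0 | s = 1 | s = 2 | s = 3 |
|---|---|---|---|---|
| 0.2 | 0% | 0.2/0.4 = 50% | 0.4/0.6 = 67% | 0.6/0.8 = 75% |
| 0.4 | 0% | 0.2/0.6 = 33% | 0.4/0.8 = 50% | 0.6/1.0 = 60% |
| 0.8 | 0% | 0.2/1.0 = 20% | 0.4/1.2 = 33% | 0.6/1.4 = 43% |

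A background of 0.4 per year means two non-planned stays among the 10 subjects in the window (2/5). If b is zero, any s of 1 or more gives an apparent 100% reduction.

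**How likely is s ≥ 1?** For an assumed planned-surgery rate r per person-year, the chance is 1 − exp(−5r). It is 22% at r = 0.05, 39% at r = 0.1 and 63% at r = 0.2. If the 4-week period in the lead-in to 5.5 also kept surgery out of the end of the window, person-time falls to 10 × 22.09/52.18 = 4.23 years. The chances then become 19%, 35% and 57%.

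**After the change.** With planned-procedure events left out of both periods, both rates equal b, and the apparent reduction is 0% for every s.

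**Anemia endpoint.** The same formula applies, but s then counts only operations that led to pseudotumor-related anemia needing transfusion or intervention.

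**The case against.** The strongest reply is that the plan never says these stays count. Sections 3.1.1 and 4.2 describe what is collected, whereas the endpoints are limited to pseudotumor-related events. Section 6.2 speaks of complications, and a planned excision is treatment. This is fair: that such a stay would be counted is an inference from silence. It does not close the gap, because in an open-label study the decision is then made afterwards, without a rule.

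A reader might go further and infer that planned surgery is barred on study, so that two primary endpoints must fall by rule. The documents do not support that:
- Section 4.3 is an entry criterion about surgery already planned, and 5.5 is permissive in wording.
- Minor procedures and emergency surgery are exempt. Incision and drainage is named as exempt in both sections, so it does not belong to the affected class.
- On-study surgery is foreseen. It has a planned/unplanned field (3.1.5), and it is a secondary objective (2.2) and a secondary endpoint (6.10.2). Section 6.11.2.2 also anticipates emergent surgery and amputation.

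Nor does any section require a subject to withdraw in order to have surgery, so a hidden loss of such admissions is speculation.

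Three further points stand in part. Entry requires an imaging-confirmed pseudotumor whose size is then followed, so a recently and completely excised lesion fits poorly. The bleed endpoint concerns breakthrough bleeds, and nothing says peri-operative bleeding counts as such; its baseline may also be as short as 16 weeks. Finally, per-subject listings for about 10 subjects would let a careful reader spot a surgical stay, though the aggregate comparison would still include it.

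**Conclusion.** The concern holds in conditional form. The two periods are not governed by one event definition, and the mismatch can work only in the drug's favor. It takes effect only if at least one subject had a planned excision or debulking in the 6 months before entry and the stay was judged pseudotumor-related. If none did, the bias from this source is zero.

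At an assumed background of 0.4 admissions per person-year, 1, 2 or 3 such stays produce an apparent fall of 33%, 50% or 60%. Over backgrounds of 0.2 to 0.8 the range is 20% to 75%. Both the background and the number of stays are assumptions. The anemia endpoint is affected only where the surgery caused the anemia. For the bleed endpoint, the point matters only if a peri-operative bleed is counted as a breakthrough bleed. The documents do not support saying that the endpoints will fall, only that they can.

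**What to change.** In 9.5:
- Classify every pre-study and on-study pseudotumor-related admission and anemia/transfusion event as part of a planned procedure or not. Do the same for any peri-operative bleed counted as a breakthrough bleed. Use the screening review of surgeries (3.1.1) and the planned/unplanned field (3.1.5).
- Base the before/after comparison on events that are not part of a planned procedure, in both periods.
- List planned-procedure events separately by period.
- List descriptively any withdrawal made in order to have pseudotumor surgery. Do not count it as an admission, since that would impute an event on one side only.

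Sections 3.1.5, 4.3 and 5.5 should also be reconciled on the status of planned and elective surgery during the study.

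The cost is a few sentences, using surgery information the plan already reviews or records. The downside is small: fewer baseline events and possibly a less favorable apparent reduction. If no subject had planned surgery in either period, the results do not change.
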